5.4.3. Supportive Care Guidelines for Neutropenia and Thrombocytopenia

Neutropenia and thrombocytopenia appear to be PI3Kδ class-effect toxicities. Investigators should ensure that subjects understand the need to seek medical care when they have conditions that could become life-threatening in the presence of cytopenias (eg, neutropenic fever or bleeding with low platelets). Subjects should be instructed to report immediately any signs of infection, unexpected bleeding, or sudden, extremely painful headaches.

5.4.4. Definition for Immune-Related Adverse Events

Adverse events of a potential immunologic etiology, or irAEs, may be defined as an AE consistent with an immune phenomenon associated with study treatment exposure after all other etiologies have been eliminated. Immune-related AEs may be expected based on previous experience with INCB050465. Special attention should be paid to AEs that may be suggestive of potential irAEs. Based on emerging data from the ongoing Study INCB 50465-101, most irAEs occur after the first 9 weeks of study treatment administration. However, an irAE could occur at any time. Suspected irAEs should be discussed with the medical monitor when possible.

Subjects should receive appropriate supportive care measures as deemed necessary by the treating investigator. Suggested supportive care measures for the management of drug-related AEs with potential immunologic etiology are outlined in Table 3 and Section 5.4.1. For each

AE, attempts should be made to rule out other causes, including but not limited to metastatic disease or bacterial or viral infection, which might require specific supportive care.

5.5. Study Treatment Discontinuation

The decision to discontinue study treatment will not constitute study completion. In the event that study treatment is discontinued, the treatment period will be considered complete, and the follow-up periods will begin.

5.5.1. Criteria for Study Treatment Discontinuation

Subjects **must** be withdrawn from study treatment for any 1 of following reasons:

- The subject has experienced an unacceptable toxicity defined as follows:
 - Occurrence of an AE that is related to study treatment that, in the judgment of the investigator or the sponsor's medical monitor, compromises the subject's ability to continue study-specific procedures or is considered to not be in the subject's best interest.
 - Persistent AE requiring a delay of therapy for more than 2 weeks (14 days) unless a greater delay has been approved by the sponsor.
- The subject is unable to tolerate study treatment.
- The subject has an objective radiographic tumor response of PD.
- Further participation would be injurious to the subject's health or well-being, in the investigator's medical judgment.
- The subject becomes pregnant.
- Informed consent is withdrawn.
Note: Consent withdrawn means that the subject can no longer be followed. Subjects may choose to discontinue study treatment and remain in the study to be followed for disease progression and survival per the schedule of assessments.
- The study is terminated by the sponsor.
- The study is terminated by the local health authority, IRB, or IEC.

A subject **may** be discontinued from study treatment in the following situations:

- If a subject is noncompliant with study procedures or study treatment administration in the investigator's opinion, then the sponsor should be consulted for instruction on handling the subject.

5.5.2. Procedures for Study Treatment Discontinuation

Reasonable efforts should be made to have the subject return for a follow-up visit. These visits are described in Section 6.4. The last date of the last dose of study treatment and the reason for subject withdrawal will be recorded in the eCRF.

If a subject permanently discontinues study treatment, then the following should occur:

- The reason(s) for discontinuation must be documented in the subject's medical record and in the eCRF.
- The EOT visit should be performed.
 - If the EOT visit coincides with a regular study visit, then the EOT evaluations will supersede those of that scheduled visit, and the data will be entered in the EOT visit in the eCRF.
- The date of the EOT visit should be recorded in the IWRS.
- Subjects must be followed for safety for no less than 30 days after the EOT visit or until study drug-related toxicities resolve, return to baseline, or are deemed irreversible, whichever is longest.

If the subject discontinues study treatment and actively withdraws consent for collection of follow-up data (safety follow-up or disease assessment), then no additional data will be collected. However, subjects may withdraw consent for study treatment but continue to be assessed for disease progression and survival per the schedule of assessments.

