6. STUDY ASSESSMENTS

All study assessments will be performed as indicated in the schedule of assessments ([Table 6](#)), and all laboratory assessments will be performed as indicated in [Table 7](#). All assessments mandated throughout the study must be performed on a calendar schedule; delays in treatment administration will not delay performance of assessments. By convention, Week 4, Week 8, Week 12, etc, means the completion of 4, 8, or 12 weeks, respectively. [Table 8](#) presents a summary of clinical laboratory analytes to be assessed. The order of assessments is suggested by the order of mention within the schedule of assessments. See [Section 7](#) for instructions on each assessment.

Table 6: Schedule of Assessments

Procedure	Section	Screening	Treatment			EOT	Follow-Up		
		Days -28 to -1	Day 1 ^a	Every 4 Weeks Through Week 48 (± 3 Days)	Every 12 Weeks From Week 48 (± 1 Week)		Safety	Disease	Survival
							EOT + 30-35 Days		Every 12 Weeks (± 1 Week)
Informed consent	7.1	X							
Contact IWRS	7.2	X	X	X	X	X			
Inclusion and exclusion criteria	3	X	X						
Demography and medical history	7.3	X							
Prior/concomitant medications	7.4	X	X	X	X	X	X		
AE assessment ^d	8.1	X	X	X	X	X	X		
Comprehensive physical exam	7.5.2	X ^e				X			
Disease-specific physical exam	7.5.3		X	X	X		X		
Vital signs	7.5.4	X	X	X	X	X	X		
12-lead ECG	7.5.5	X	X ^f	X ^f	X	X	X		
ECOG performance status	7.5.6	X	X	X	X	X	X		
CT/MRI scan	7.6.1	X		Every 8 weeks through Week 24 (± 1 week), then every 12 weeks through Week 96, and then every 24 weeks thereafter until PD				X ^e	
Bone marrow exam	7.6.2	X ^g			X ^h			X ^h	
Prophylactic treatment for PJP	5.6.1			X ⁱ					
Study treatment dispensing	5.1.1		X	X	X				
Study treatment compliance	5.3		X	X	X	X			
INCB050465 administration	5.2.1		X	X	X				
Disease follow-up	6.4.2							X ^e	
Survival follow-up	6.4.3							X ^j	

^a All procedures are to be performed before administration of study treatment on Day 1.

^d Adverse events will be monitored from the time the subject signs the ICF until at least 30 days after the last dose of study treatment. Serious AEs occurring more than 30 days after the last dose of study treatment should be reported to the sponsor or its designee if the investigator suspects a causal relationship to the study treatment. Once detected, AEs should be followed until resolved or judged to be permanent.

^e Height required at screening only.

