6.3. End of Treatment

There is no defined date of EOT. When the subject permanently discontinues study treatment, then the EOT visit should be conducted. If the EOT visit coincides with a regular study visit, the EOT evaluations will supersede those of that scheduled visit, and the data should be entered in the EOT visit in the eCRF. The subject should be encouraged to return for the safety follow-up visit.

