6.4. Follow-Up

6.4.1. Safety Follow-Up

The safety follow-up period is the interval between the EOT visit and the scheduled follow-up visit, which should occur 30 to 35 days after the EOT visit (or after the last dose of study treatment if the EOT visit was not performed). Adverse events and SAEs must be reported up until at least 30 days after the last dose of study treatment, the date of the follow-up visit, or until toxicities resolve, return to baseline, or are deemed irreversible, whichever is longer. Reasonable efforts should be made to have the subject return for the follow-up visit and report any AEs that may occur during this period.

If a subject is scheduled to begin a new anticancer therapy before the end of the safety follow-up period, then the safety follow-up visit should be performed before new anticancer therapy is started. Once new anticancer therapy has been initiated, the subject will move into the survival follow-up period.

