When the severity of an AE changes over time for a reporting period (e.g., between visits), each change in severity will be reported as a separate AE until the event resolves. For example, 2 separate AEs will be reported if a subject has Grade 1 diarrhea, meeting the definition of an AE, that lasts for 3 days before worsening to a Grade 3 severity. The Grade 1 event will be reported as an AE with a start date equal to the day the event met the Grade 1 AE definition and a stop date equal to the day that the event increased in severity from Grade 1 to Grade 3. The Grade 3 event will also be reported as an AE, with the start date equal to the day the event changed in intensity from Grade 1 to Grade 3 and a stop date equal to the day that the event either changed severity again or resolved.

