### 9.2. Adverse Events

#### 9.2.1. Adverse Event Definitions

A TEAE is any AE either reported for the first time or worsening of a pre-existing event after first dose of study drug and within 30 days of the last administration of study drug regardless of starting new anti-lymphoma therapy. Analysis of AEs (as discussed below) will be limited to TEAEs, but data listings will include all AEs regardless of their timing in relation to study drug administration. For purposes of analysis, all AEs will be considered TEAEs unless the AE can unequivocally be defined as not treatment-emergent.

Adverse events will be tabulated by MedDRA PT and SOC. Severity of AEs will be graded using the NCI CTCAE version 4.03. The CTCAE reporting guidelines and grading details are available on the Cancer Therapy Evaluation Program website.

The subset of AEs considered by the investigator to be related to study drug will be considered to be treatment-related AEs. If the investigator does not specify the relationship of the AE to study drug, the AE will be considered to be treatment-related. The incidence of AEs and treatment-related AEs will be tabulated. In addition, serious TEAEs will also be tabulated.

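### AE tables stop 30 days after last dose, so an on-treatment AE that worsens later, with dosing never resumed, is tabulated at its lower grade

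*Protocol*

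**What the plan says.** **Collection.** Protocol 5.5.2 states: "Subjects must be followed for safety for no less than 30 days after the EOT visit or until study drug-related toxicities resolve", with return to baseline or irreversibility as the other end points and the longest period applying. Section 6.4.1 schedules the safety visit, "which should occur 30 to 35 days after the EOT visit", and takes AE reporting to at least 30 days after last dose, to that visit, "or until toxicities resolve, return to baseline, or are deemed irreversible, whichever is longer". The end-of-treatment (EOT) visit is tied to the decision to stop, not to the last dose. Protocol 6.3: "When the subject permanently discontinues study treatment, then the EOT visit should be conducted". Under 5.5.1 one ground for stopping is: "Persistent AE requiring a delay of therapy for more than 2 weeks (14 days) unless a greater delay has been approved by the sponsor".

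**Recording.** Protocol 8.1.2: "each change in severity will be reported as a separate AE until the event resolves". Its worked example dates the worse record to the day the grade changed.

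**Counting.** SAP 9.2.1 defines a treatment-emergent AE (TEAE) as one first reported, or a pre-existing one that worsens, "after first dose of study drug and within 30 days of the last administration of study drug regardless of starting new anti-lymphoma therapy". Protocol 9.4.2.1 has the same 30-day limit. Both restrict AE analysis to TEAEs and leave other AEs to listings. SAP 9.2.1 adds that an AE counts as a TEAE unless it clearly is not one. In SAP 9.2.2, time to onset for participants without the event is censored no later than day 30 after last dose. Duration of a non-serious TEAE can run to the safety visit or 35 days after the EOT visit.

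**The concern.** Collection is anchored to the EOT visit or to resolution, while tabulation is anchored to the last dose. The two anchors separate whenever drug is held before the decision to stop. Because the Protocol splits an AE at each grade change, the worse part of a single clinical episode can fall outside the counting window while its milder part stays inside.

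The setting is one the Protocol itself foresees. Protocol 5.4.2 warns that diarrhea or colitis may need several steroid tapers because symptoms can return as the dose falls. Table 5 makes restart wait for the taper to finish.

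At stake are the maximum-severity, Grade 3 or higher, serious and fatal-outcome tables of SAP 9.2.3 and the special-interest AE table of SAP 9.2.2. AEs that lead to withdrawal are the stated reason for testing these two regimens (Protocol 1.4 and 1.5), so the worst grade of such AEs is a result readers will look for.

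**Working it through.** The plan states no figure on this point, so there is none to reproduce. The check is date arithmetic.

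**Inputs**
- Safety visit: EOT visit + 30 to 35 days (Protocol 6.4.1).
- TEAE window: closes 30 days after last dose (Protocol 9.4.2.1, SAP 9.2.1).
- Hold: up to 14 days; a longer one calls for withdrawal unless the sponsor approves it (Protocol 5.4.1, 5.5.1).
- Cohort 2: up to 90 participants (Protocol 9.2).

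**Formula.** Let day 0 be the last dose and h the days from last dose to the EOT visit. The safety visit falls on day h + 30 to h + 35. Days collected but outside the window = (h + 30) − 30 to (h + 35) − 30 = h to h + 5.

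| h | Safety visit, day after last dose | Days outside window |
|---|---|---|
| 0 | 30–35 | 0–5 |
| 7 | 37–42 | 7–12 |
| 14 | 44–49 | 14–19 |
| 28 | 58–63 | 28–33 |

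The row h = 28 is an assumption; a hold of that length needs sponsor approval. Toxicity followed to resolution can extend the collected span further.

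**One case traced through.** Grade 2 diarrhea starts on treatment, drug is held and never restarted, and the EOT visit is on day 14.
- Worsening to Grade 3 on day 10, 25 or 30: the new record starts inside the window and is a TEAE.
- Worsening on day 31, 40 or 49: the new record starts outside the window. Maximum severity stays at Grade 2, and the Grade 3 or higher table omits the participant for this event.

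The default in SAP 9.2.1 does not rescue the second group. It resolves doubt about timing, and a fully dated record after day 30 leaves none.

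**Effect of one case.** 1/90 = 1.1 points, 1/60 = 1.7 points, 1/30 = 3.3 points. As an illustration only, 0/90 has an exact upper 95% limit of 4.0%, and 1/90 has 6.0%.

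**The case against.** **It is a consistent, pre-specified choice.** A reader might infer that the SAP departs from the Protocol. It does not: the 30-day rule is in both, and SAP Amendment 2 revisited 9.2.1 and kept it. Following events to resolution while tabulating over a fixed post-dose window is common practice. This stands, and the 30-day limit for new AEs should stay. It does not explain why the later part of an episode that began inside the window should be cut off.

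**Few cases qualify.** A reader might infer that any worsening after a hold is lost. Worsening by day 30 is counted, and if dosing resumes the last dose moves later and so does the window. Where Protocol Table 3 requires immediate permanent discontinuation, h is near 0 and the gap is about 0 to 5 days. This stands.

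**Nothing is discarded.** Late records remain in the AE, serious, Grade 3 or higher, treatment-related and fatal listings. Deaths enter overall survival. Laboratory shift tables use the worst postbaseline grade with no stated 30-day cut. This stands; the loss is confined to the AE incidence tables.

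**The serious and fatal tables may be less affected.** Protocol 8.3.2 has progression of an SAE reported as follow-up to that event, and 8.1.2 lists fatal as an event outcome. If a site enters a late death as the outcome of the existing record, it would be tabulated. This stands in part. Section 8.3.2 governs the SAE report form, while 8.1.2 governs the grade-split AE record, and the SAP does not say which prevails. The Grade 3 or higher limb does not depend on this.

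**Size.** In Study 101, 14/72 (19.4%) stopped for AEs. Applied to 90 this gives about 17, and a reader might take that as the number at risk. It is all expected AE discontinuations, from once-daily dosing at 5 to 45 mg, most of which need not involve a hold followed by late worsening.

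**Conclusion.** The point holds in a limited form. With dosing never resumed, an AE that began on treatment and worsens more than 30 days after the final dose is tabulated at its lower grade. The worse record appears only in listings, apart from deaths in overall survival. If the EOT visit falls 14 days after last dose, 14 to 19 days of collected follow-up are exposed to this. Each affected participant moves a rate by 1.1 points at n = 90. The documents do not give the number affected, and they do not show that the under-count is large or concentrated in one regimen.

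The conclusion assumes that sites split records by grade as 8.1.2 directs and that onset dates are complete.

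A reader might also infer that every suspected-related event after day 30 should become a TEAE. Protocol Table 6, footnote d, provides: "Serious AEs occurring more than 30 days after the last dose of study treatment should be reported to the sponsor or its designee", on condition that the investigator suspects a causal link; 8.3.2 says only then. Late reporting is therefore selective. In an open-label study such a window would have no end and would rest on investigator causality. Blank causality counts as related under SAP 9.2.1, and SAP 9.2.2 censors everyone else by day 30. The documents do not support that step.

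**What to change.** In SAP 9.2.1, keep the 30-day window for new AEs and add one rule. A record that is a contiguous grade change of an AE whose first post-dose onset or worsening fell inside the window belongs to that TEAE, whatever its own start date. Its worst grade, seriousness and outcome then enter the incidence tables of SAP 9.2.2 and 9.2.3. Under Protocol 8.1.2 the new record starts on the day the previous one stops, so records can be chained from data already collected.

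Three companion edits:
- List the rule in SAP 11.1, now marked not applicable, as a change to Protocol 9.4.2.1.
- Keep the time-to-onset analyses in SAP 9.2.2 cut at day 30 for events and censoring alike, and footnote the difference from the incidence tables.
- Show suspected-related AEs or SAEs that first start after day 30 in a separate supplementary summary, not as TEAEs.

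The cost is a small programming rule and one extra summary. Grade 3 or higher, serious and fatal counts may rise slightly. No dosing, hold or follow-up rule changes.

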5.6. Concomitant Medications

All concomitant medications and treatments must be recorded in the eCRF. Any prior medication received up to 30 days before the date of study treatment administration (Day 1) will be recorded in the eCRF. Concomitant treatments and/or procedures that are required to manage a subject's medical condition during the study will also be recorded in the eCRF.

5.6.1. *Pneumocystis Jirovecii* Pneumonia Prophylaxis

All subjects are required to receive a standard PJP prophylaxis regimen determined by the investigator (see Section 5.2.2). Examples of standard PJP prophylaxis therapies for this population include trimethoprim-sulfamethoxazole, atovaquone, dapsone with or without pyrimethamine, and pentamidine (NCCN 2017). Due to reports of cross-sensitivity between sulfonamides and dapsone, all subjects who have a known or suspected allergy to sulfonamides must receive either inhaled pentamidine or atovaquone for PJP prophylaxis. Prophylaxis should be given while subjects are receiving study treatment and should continue for at least 2 to 6 months after the last dose of study treatment.

5.6.2. Restricted Medications

- Use of systemic corticosteroid doses ≤ 10 mg/day prednisone (or equivalent) is permitted but discouraged from the screening visit through EOT.
- Short courses of systemic corticosteroid doses > 10 mg/day prednisolone or equivalent are permitted only in the case of severe or life-threatening complications, which cannot be controlled with other drugs, but are otherwise discouraged from the screening visit through EOT.
- Use of weak or moderate inducers or inhibitors of CYP3A4 (see Appendix D) is discouraged, and investigators should seek other options where possible.

- Use of P-glycoprotein substrates of clinical relevance should be used with caution (ie, aliskiren, ambrisentan, colchicine, dabigatran etexilate, digoxin, everolimus, fexofenadine, imatinib, lapatinib, maraviroc, nilotinib, posaconazole, ranolazine, saxagliptin, sirolimus, sitagliptin, talinolol, tolvaptan, topotecan) from the screening visit through the EOT visit.
- Localized radiotherapy will be permitted if administered as treatment for pain or impending compression fractures and with prior approval of the medical monitor.

5.6.3. Prohibited Medications

- Use of potent inducers and inhibitors of CYP3A4 is prohibited (see [Appendix D](#)). Based on the low overall bioavailability of topical ketoconazole, there are no restrictions on topical ketoconazole.
- Apart from the study treatments, the use of any anticancer medications as described (see Section 3.2) through the 30-day follow-up is prohibited.
- Exposure to a live vaccine within 30 days of study treatment through 3 months after the last dose of INCB050465.

5.7. Criteria for Study Discontinuation

A subject will be discontinued from the study for any 1 of the following reasons:

- The subject has died.
- The subject is considered lost-to-follow-up when he/she repeatedly fails to return for scheduled visits and is unable to be contacted by the study site (eg, after 3 telephone calls and/or a certified letter or local equivalent).
- Informed consent is withdrawn.
- The study is terminated by the sponsor.
- The study is terminated by the local health authority, IRB or IEC.

5.8. Treatment After the End of the Study

At the end of the study as defined in Section 6.5, subjects who have completed at least 24 months of study participation (starting from the first dose of study treatment), who remain on active study treatment, and who have no evidence of progressive disease will have the option to continue on monotherapy with INCB050465 provided within a rollover Protocol, as local law permits.

6. STUDY ASSESSMENTS

All study assessments will be performed as indicated in the schedule of assessments ([Table 6](#)), and all laboratory assessments will be performed as indicated in [Table 7](#). All assessments mandated throughout the study must be performed on a calendar schedule; delays in treatment administration will not delay performance of assessments. By convention, Week 4, Week 8, Week 12, etc, means the completion of 4, 8, or 12 weeks, respectively. [Table 8](#) presents a summary of clinical laboratory analytes to be assessed. The order of assessments is suggested by the order of mention within the schedule of assessments. See [Section 7](#) for instructions on each assessment.

Table 6: Schedule of Assessments

Procedure	Section	Screening	Treatment			EOT	Follow-Up		
		Days -28 to -1	Day 1 ^a	Every 4 Weeks Through Week 48 (± 3 Days)	Every 12 Weeks From Week 48 (± 1 Week)		Safety	Disease	Survival
							EOT + 30-35 Days		Every 12 Weeks (± 1 Week)
Informed consent	7.1	X							
Contact IWRS	7.2	X	X	X	X	X			
Inclusion and exclusion criteria	3	X	X						
Demography and medical history	7.3	X							
Prior/concomitant medications	7.4	X	X	X	X	X	X		
AE assessment ^d	8.1	X	X	X	X	X	X		
Comprehensive physical exam	7.5.2	X ^e				X			
Disease-specific physical exam	7.5.3		X	X	X		X		
Vital signs	7.5.4	X	X	X	X	X	X		
12-lead ECG	7.5.5	X	X ^f	X ^f	X	X	X		
ECOG performance status	7.5.6	X	X	X	X	X	X		
CT/MRI scan	7.6.1	X		Every 8 weeks through Week 24 (± 1 week), then every 12 weeks through Week 96, and then every 24 weeks thereafter until PD				X ^e	
Bone marrow exam	7.6.2	X ^g			X ^h			X ^h	
Prophylactic treatment for PJP	5.6.1			X ⁱ					
Study treatment dispensing	5.1.1		X	X	X				
Study treatment compliance	5.3		X	X	X	X			
INCB050465 administration	5.2.1		X	X	X				
Disease follow-up	6.4.2							X ^e	
Survival follow-up	6.4.3							X ^j	

^a All procedures are to be performed before administration of study treatment on Day 1.

^d Adverse events will be monitored from the time the subject signs the ICF until at least 30 days after the last dose of study treatment. Serious AEs occurring more than 30 days after the last dose of study treatment should be reported to the sponsor or its designee if the investigator suspects a causal relationship to the study treatment. Once detected, AEs should be followed until resolved or judged to be permanent.

^e Height required at screening only.

^f Timed triplicate ECGs will be obtained during the Day 1 visit (predose) and Week 4 visit (predose and 1.5 hours [\pm 15 minutes] after receiving study treatment).

^g Required at baseline except for reasons provided in Section 7.6.2.

^h If disease is present in bone marrow at baseline, a bone marrow biopsy will be required to confirm CR or may be performed as clinically indicated. For subjects with splenic MZL without measurable disease (ie, only have histologically confirmed bone marrow infiltration), a bone marrow biopsy/examination must be performed when the number of lymphocytes in the blood normalize.

ⁱ *Pneumocystis jirovecii* pneumonia prophylaxis should be given while subjects are receiving study treatment and continue for at least 2 to 6 months after the last dose of study treatment.

^j May be conducted by clinic visit, telephone, or email.

Table 7: Schedule of Laboratory Assessments

Laboratory Tests ^a	Section	Screening	Treatment				EOT	Safety Follow-Up
		Day -28 to -1	Day 1 ^b	Every 4 Weeks Through Week 48 (± 3 Days)	Every 12 Weeks From Week 48 (± 1 Week)	Other		EOT + 30-35 Days
Serum chemistries	7.5.7.1	X	X ^c	X	X		X	X
Hematology ^d	7.5.7.1	X	X ^c	X	X	X ^e	X	X
Serology	7.5.7.3	X		X ^f	X ^f			
HIV testing	7.5.7.3.1	X ^g						
Serum pregnancy	7.5.7.2	X ^h					X	
Urine pregnancy	7.5.7.2					X ⁱ		
Tumor/bone marrow biopsy	7.8.5	X ^m				X ⁿ		

^a All laboratory assessments must be performed at a central laboratory, unless otherwise specified (see Section 7.5.7).

^b All laboratory assessments are to be performed before administration of study treatment on Day 1, unless otherwise specified.

^c If chemistry and/or hematology laboratory assessments occurred in the preceding 7 days, Day 1 assessments may be omitted.

^d Hematology will be collected every 2 weeks for the first 8 weeks.

^e Week 2 (Day 15) and Week 6 (Day 43) ± 3 days.

^f Samples for CMV DNA analysis only.

^g Optional for subjects enrolled in the United States.

^h Only for females of childbearing potential; negative serum pregnancy test must be obtained within 14 days before administration of study treatment. Screening test may be performed centrally or at the investigative site laboratory.

ⁱ Only for females of childbearing potential; if a urine pregnancy test is positive, then a serum pregnancy test should be performed. Urine pregnancy must be collected every 4 weeks until last dose of study treatment.

[REDACTED]

Table 8: Laboratory Tests: Required Analytes

Serum Chemistries	Hematology	Serology	
Albumin	Complete blood count, including: Hemoglobin Hematocrit Platelet count (absolute) Red blood cell count White blood cell count Differential count, including: Basophils Eosinophils Lymphocytes Monocytes Neutrophils Absolute values must be provided for: WBC differential laboratory results: Lymphocytes Neutrophils	Hepatitis B surface antigen Hepatitis B surface antigen antibody Hepatitis B core antibody HBV-DNA HCV antibody HCV-RNA CMV DNA HIV antibody (immunoassay) ^a	
Alkaline phosphatase			
ALT			
AST			
Bicarbonate			
Blood urea nitrogen			
C-reactive protein			
Calcium			
Chloride			
Creatinine			
Glucose			
Lactate dehydrogenase			
Phosphate			
Potassium			
Sodium			
Total bilirubin			
Direct bilirubin (if total bilirubin is > ULN)			
Total protein			
Uric acid			
		Pregnancy Testing	
		Only for female subjects of childbearing potential Pregnancy tests (serum or urine) should be repeated if required by local regulations.	

Note: Additional tests may be required, as agreed by investigator and sponsor, based on emerging safety data.

^a Optional for subjects enrolled in the United States.

